SphygmoCor Xcel is a class-II FDA approved device used in clinical and research settings. SphygmoCor is a non-invasive, cuff-based tool used for obtaining brachial artery blood pressure and the central arterial pressure waveform with associated indices (augmentation index, augmentation pressure, and pulse wave velocity). A cuff will be applied on the upper arm in the standard position. The cuff will be partially inflated to record the brachial waveforms. These waveforms are detected by sensing changes in the pressure inside the cuff related to arterial pulsation. The ascending aortic waveform is subsequently derived using a validated mathematical transfer function.

The participant may be provided with their current blood pressure and heart rate, as measured by this FDA approved device.

Questionnaires

Self-reported interview-style questionnaires are quick, convenient and reliable source of research data collection. This modality is used by many large NIH funded research studies like the Multi-Ethnic Study of Atherosclerosis (MESA), the National Health and Nutrition Examination Survey (NHANES), and many of our group's other NIH funded studies – the Green Heart Project, Cardiovascular Injury in Tobacco, Louisville Healthy Heart Study, etc. We will utilize these existing questionnaires (internal and external) to compile a list of relevant questions which will help in high quality data acquisition. The questionnaires will collect data on medical history, medications, environmental pollution exposure, sleep, diet, exercise, tobacco, and women's health.

Data will be recorded in real-time in a REDCap database created specifically for this study. Since, these questionnaires will collect multiple personal information and PHI, only trained research personnel with relevant reason will be granted access.

Physical Examination

[figure not shown]
Physical examination will be conducted to record the participant's height, weight, and waist circumference. Blood pressure and heart rate measurements will be provided during the arterial stiffness measurement.

Physical Function Test

To assess the impact of carnosine supplementation on physical performance during times of variable PM_{2.5} levels, we will utilize three physical performance tests: handgrip

Carnosine NEAT Trial Protocol
Version Date 5-14-2020

Page 21 of 82

strength test, 2-minute step test (2MST), and bilateral calf-raise test. The protocol for these measurements are further detailed in Appendix E.

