5. **Low blood pressure:** Carnosine synthesized in the body has been found to decrease blood pressure via influencing the autonomic nervous system.⁴³ Hence, in theory, taking supplemental carnosine might lower blood pressure and or exacerbate lowering of blood pressure in people taking antihypertensive medications. Hence, all participants taking blood pressure lowering medication will be cautioned for this interaction and advised that in case of an episode of low blood pressure to discontinue study supplement and immediately seek medical attention from a licensed healthcare provider.
6. **Low blood sugar:** Carnosine synthesized in the body has been found to decrease blood sugar via influencing the autonomic nervous system.⁴³ Hence, in theory, taking supplemental carnosine might lower blood sugar and or exacerbate lowering of blood sugar in people taking blood sugar lowering medications. Hence, all participants taking blood sugar lowering medication will be cautioned for this interaction and advised that in case of an episode of low blood sugar to discontinue study supplement and immediately seek medical attention from a licensed healthcare provider.

Participants will be advised to continue / discontinue after a review by the study physician and the DSMB.

[figure not shown]

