12. CLINICAL AND LABORATORY EVALUATIONS

Schedule of Procedures

Study Activities	Screening (Visit # 1)	Screening (Visit # 2)	Screening (Visit # 3)	Screening (Visit # 4)	4-12 Month Safety Check
Informed Consent	X				
Contact & Demographics	X	X	X	X	
Medical History		X	X	X	X
Medications History		X	X	X	X
Physical Exam		X	X	X	
Blood Samples		X	X	X	
Urine Samples	X	X	X	X	
Arterial Stiffness Exam		X	X	X	
Physical Function Exam		X	X	X	
Environmental Pollution Exposure Questionnaire		X	X	X	
Sleep Questionnaire		X	X	X	
Diet & Exercise Questionnaire		X	X	X	
Supplement Distribution		X	X		
Adverse Events Check			X	X	X
Checkout (Prepaid Visa)	X	X	X	X	

Procedure Details

Contact and Demographics

A detailed account of the participant's contact and demographic information will be collected at screening (Visit # 1). This information will be critical while implementing the screening criteria and selecting eligible candidates for randomization. This information is also required for NIH progress report reporting. It will be administered by a research team member at every clinical study visit (Visit # 1 through # 4).

Participant Medical History and Physical Exam

A complete participant history including medical, alcohol, tobacco, and medication review will be conducted at baseline assessment (Visit # 2).

A complete physical exam including vitals, height, and weight will be completed at baseline assessment (Visit # 2). Similar physical exams will be conducted at each additional clinic visit (Visit # 3 and Visit # 4) during the study.

Blood and Urine Samples

[figure not shown]
A fresh catch urine sample will be collected at screening (Visit # 1). Urine sample collection details are in Section 8 “Investigational Plan” and Appendix A. This is necessary to identify the candidate’s body carnosine level and to implement the inclusion criteria. This information is critical in screening and selecting eligible candidates for randomization. A fresh catch urine sample will be collected by a research team member at every clinical study visit (Visit # 1 through # 4).

Fresh stick blood samples will be collected at baseline assessment (Visit # 2). Blood sample collection details are in Section 8 “Investigational Plan” and Appendix A. Fresh stick blood samples will be collected at each additional clinical study visit from baseline onwards (Visit # 2 through Visit # 4).

Arterial Stiffness Test

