SphygmoCor will be used to measure indices of arterial stiffness (augmentation index; AI, augmentation pressure; AP, pulse wave velocity; PWV, aortic systolic pressure, and SEVR).

SphygmoCor is a non-invasive, cuff-based tool used for obtaining brachial artery blood pressure and the central arterial pressure waveform with associated indices (augmentation index, augmentation pressure, and pulse wave velocity). A cuff will be applied on the upper arm in the standard position. The cuff will be partially inflated to record the brachial waveforms. These waveforms are detected by sensing changes in the pressure inside the cuff related to arterial pulsation. The ascending aortic waveform is subsequently derived using a validated mathematical transfer function.

Arterial stiffness test will be administered by a research team member at baseline assessment (Visit # 2) and then at each additional clinical study visit from baseline onwards (Visit # 2 through Visit # 4). Arterial stiffness testing (via SphygmoCor) is detailed in Section 8 “Investigational Plan”.

Physical Function Test

To assess the impact of carnosine supplementation on physical performance during times of variable PM_{2.5} levels, we will utilize three physical performance tests: handgrip strength test, 2-minute step test (2MST), and bilateral calf-raise test.

Physical function test will be administered by a research team member at baseline assessment (Visit # 2) and then at each additional clinical study visit from baseline onwards (Visit # 2 through Visit # 4). Testing protocol is detailed in Section 8 “Investigational Plan” and Appendix E.

Environmental Pollution Exposure Questionnaire

This questionnaire will assess participant’s exposure to environmental pollution. It will be administered by a research team member at baseline assessment (Visit # 2), Follow-Up # 1 (Visit # 3) and Follow-Up # 2 (Visit # 4).

Sleep Questionnaire

This questionnaire will assess participant’s sleep habits during the study period. It will be administered by a research team member at baseline assessment (Visit # 2), Follow-Up # 1 (Visit # 3) and Follow-Up # 2 (Visit # 4).

[figure not shown]
Diet and Exercise Questionnaire

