The events listed below will follow the same reporting criteria for SAE/SSARs as it relates to the PI as well as the CTU and are to be considered sufficient to halt the study procedure. If subject develops any of the following conditions within 48 hours of planned supplement consumption, study supplement delivery will be halted in that particular participant:

[figure not shown]
1. Diarrhea / Vomiting / Stomach Upset
2. Sudden drop in blood pressure
3. Sudden drop in blood sugar
4. Hemodynamically unstable

Holding Rules

The expected number of SAE/SSARs in this trial is anticipated to be too small to support formal statistical stopping rules. However, the following criteria are provided as guidelines under which this **clinical trial may be put on hold pending a detailed investigation by the DSMB**. The assessment of the event shall include the relationship to the trial procedures as unrelated or possibly related. If possibly related, an indication of causality to a specific aspect of the study supplement / procedures will be determined: (e.g. study supplement consumption related, study supplement safety related, study supplement manufacturing related).

Holding Criteria

The DSMB will recommend putting the trial on hold as soon as it is notified of **one or more of holding criteria** listed below. The study holding criteria have been created under the guidelines of current literature data and the 21 CFR code of the FDA regulatory information. The study holding criteria:

1. 20% or more cases of out of the total enrollment with Diarrhea / Vomiting / Stomach Upset
2. 20% or more cases of out of the total enrollment with Sudden drop in blood pressure
3. 20% or more cases of out of the total enrollment with Sudden drop in blood sugar
4. 20% or more cases of out of the total enrollment with Hemodynamically unstable events
5. 20% or more cases of out of the total enrollment with Hospitalizations
6. Or any other reason specified by the DSMB, study EC, bulk supplier or manufacturing pharmacist

As soon as any of the above is identified, the EC will inform the IRB and the DSMB. In addition, the DSMB will monitor the distribution of all SAE/SSARs, and the PI will be responsive to all DSMB concerns regarding SAE/SSARs that are not part of holding criteria listed above.

In addition, the DSMB may also recommend stopping the trial for the performance-related issues that would prevent the study from meeting its scientific objectives, such as:

[figure not shown]

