Participants of both the groups ("A" or "B") will undergo the exact same procedures of data collection as detailed in section 10 "Study Visits". The CTU will monitor participant recruitment by providing reports to the study co-PI and DSMB as appropriate during the recruitment phase. Updated reports will be maintained on an Internet site accessible to all units of the study. The recruitment reports will provide data on recruitment of women and minorities (African-Americans, Hispanics, and Asians). Goals for recruitment will be set and will be reviewed by the PI.

Statistical Analyses

Biostatisticians at the Envirome Institute, with the assistance of bioinformatics experts, have adapted or developed a number of statistical programs for analyzing study data. Data are analyzed for both data monitoring purposes, as described above, and for the purpose of detecting effects of the supplement. The Envirome Institute uses standard statistical packages such as SAS, S-PLUS, R and Stata to perform statistical analyses.

Participants receiving supplementation will be presented. Participants receiving supplementation who are found not to have fully met the eligibility criteria will also be presented. On-study protocol violations will also be presented. Participants who do not complete the required observations will be listed and evaluated separately as necessary. Reasons for study discontinuation and date of withdrawal from study will be presented.

Baseline Analyses

Although the stratified random assignment of participants to the various supplements should ensure comparability with respect to known and unknown variables, imbalance may occur by chance. Descriptive statistics for baseline characteristics known or suspected to be associated with outcomes will be prepared for the various supplementation groups. The variables considered in such a description can be categorized as: 1) demographic characteristics; 2) medical history; 3) physical examination; and 4) laboratory data. Exact testing for categorical variables and Student *t* testing for continuous variables will be used to evaluate the differences in baseline variables between supplement groups.

Outcome Analyses

Primary and Secondary Endpoints

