There are 5 primary endpoints: difference in EPCs (EPC-2, EPC-3, EPC-4, EPC-7, and EPC-8) between Carnosine and placebo groups at 6 weeks and 12 weeks. These endpoints will be evaluated at the alpha=0.01. There are four secondary endpoints: difference in EPCs between Carnosine and placebo groups at 12 weeks, difference in EPCs between Carnosine and placebo groups at 6 weeks, difference in arterial stiffness between carnosine and placebo groups at 6 and 12 weeks, difference in endothelial microparticles between carnosine and placebo groups at 6 and 12 weeks, and difference in platelet monocyte aggregates between carnosine and placebo groups at 6 and 12 weeks.

Continuous variables will be presented by summary statistics (such as mean, median, standard error, range, 95% CI, correlations) and the categorical variables by frequency distributions (frequency counts, percentages and 95% CI). We will also calculate correlations along with confidence intervals. To identify significant differences due to intervention, we will compare the differences using a two sample t-test. We will use regression (logistic or linear) to model and test the effect of other covariates such as age and race. We also will compare outcome measures using GLM and MIXED model procedures to account of repeat observations. General statistical analyses will be performed with the SAS statistical software package (SAS Institute Inc., Cary, NC).

Statistical Monitoring Rule

[figure not shown]
Safety monitoring of the accumulated outcomes data is designed to ensure the continuing safety of the currently enrolled participants and participants not yet enrolled. This is achieved by stopping the trial early to reduce the number of participants exposed to a harmful or ineffective supplementation.

Monitoring Non-efficacious Supplementation (Futility)

We do not plan any interim analyses for futility due to longer follow-up (1 year).

Monitoring Toxic Supplementation (Safety)

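### Section 15 plans no post-baseline by-arm safety comparison of brachial blood pressure, although a drop is a named carnosine risk and the readings are already taken

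*Combined protocol and SAP*

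**What the plan says.** **The risk.** Sections 9 and 10 say that carnosine might in theory lower blood pressure, or add to the effect of antihypertensive drugs. Section 16 lists a drop in blood pressure among the possible risks. It adds that people on antihypertensives may have a temporary sudden drop, with a higher risk of stroke and heart attack while it lasts. Section 9 admits people with treated, controlled hypertension.

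**The readings.** Section 8, Physical Examination: "Blood pressure and heart rate measurements will be provided during the arterial stiffness measurement". The device is a cuff that gives brachial pressure. Section 12 schedules the stiffness test at Visits 2, 3 and 4 and says of the physical examination, which includes vitals: "Similar physical exams will be conducted at each additional clinic visit (Visit # 3 and Visit # 4) during the study".

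**The planned comparisons.** In Section 15, Baseline Analyses, exact tests and Student t tests "will be used to evaluate the differences in baseline variables between supplement groups", and physical examination is one of the variable groups. After baseline, the by-arm endpoints are EPCs, endothelial microparticles, platelet-monocyte aggregates and the "difference in arterial stiffness between carnosine and placebo groups at 6 and 12 weeks". The only safety analysis is a running count of grade 3 or 4 events against a 33% rate.

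**The safety handling.** Section 10: "Participants will be advised to continue / discontinue after a review by the study physician and the DSMB". In Section 14 a sudden drop in pressure halts supplement for that participant, and "The events listed below will follow the same reporting criteria for SAE/SSARs as it relates to the PI as well as the CTU". One holding criterion is "20% or more cases of out of the total enrollment with Sudden drop in blood pressure". The semi-annual reports are described as giving event totals for the trial overall. Section 13, Severity Assessment, keeps Grade 1 events off the eCRF. Elsewhere Section 13 asks for events to be recorded there, and Section 14 says the cumulative reports include all events.

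**The concern.** The trial names a harm and measures the relevant quantity once before supplement and twice on it, in both randomized arms. It then plans no analysis of those readings as safety data.

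The adverse-event route does not reliably fill the gap for small sustained falls. A Grade 1 event is not entered on the eCRF. An asymptomatic shift may never become an event at all: Section 13 treats endpoint tests as research measurements. It calls for a clinical-grade result to be reported when there are symptoms, a need for further tests or intervention, or a judgement by the investigator or sponsor that it is an event.

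What is at stake is what the trial can say about blood pressure when it reports, especially as treated hypertensives may enroll. The EPC results do not depend on it. If the comparison is left unspecified, whether and how to report it becomes a choice made after the data are seen.

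**Working it through.** **1. The plan's own figures.** The documents state no figure for blood pressure. The sample size does reproduce: a two-sample comparison of 0.5 SD at two-sided alpha 0.01 and 90% power needs 120 per arm (power 90.3%), and 240 / 0.6 = 400. The 120 per arm is used below.

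**2. Is the comparison planned anywhere?** Section 15 was read item by item.
- Baseline analyses cover physical examination, at baseline only.
- Primary and secondary endpoints do not include brachial pressure.
- The toxicity rule counts grade 3 or 4 events, not readings.
- Subgroup evaluations apply to the primary and secondary endpoints.
- Additional analyses concern EPCs.

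The nearest item is central pressure. Section 12: "SphygmoCor will be used to measure indices of arterial stiffness (augmentation index; AI, augmentation pressure; AP, pulse wave velocity; PWV, aortic systolic pressure, and SEVR"). Aortic systolic pressure is therefore probably compared by arm within the stiffness endpoint, but as efficacy, and Section 15 does not say which index is used.

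**3. What a by-arm comparison would deliver.** The SD of change is assumed to be 10, 12 or 14 mmHg, because the documents give none. Change scores are unadjusted.
- 95% CI half-width = t × SD × √(2/n). At n = 120 per arm, √(2/120) = 0.129 and t is about 1.97.
- Power is from the noncentral t distribution, two-sided 0.05.

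| SD of change (mmHg) | 10 | 12 | 14 |
|---|---|---|---|
| Half-width, 120 per arm | 2.5 | 3.1 | 3.6 |
| Half-width, 200 per arm | 2.0 | 2.4 | 2.8 |
| Power, 5 mmHg, 120 per arm | 97% | 90% | 79% |
| Power, 3 mmHg, 120 per arm | 64% | 49% | 38% |

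Adjusting for the Visit 2 value multiplies the half-width by √((1 + r)/2). That is 0.87 at an assumed visit-to-visit correlation of 0.5 and 0.95 at 0.8.

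**4. Why the mean difference should lead and the count support it.** Under a normal model, the chance of a fall of at least c when the mean fall is m is Φ(−(c − m)/SD). Results are for SD 10 / 12 / 14, with 120 per arm.
- c = 10, m = 0: 16 / 20 / 24%, or about 19 / 24 / 29 people per arm by chance alone.
- c = 10, m = 5: 31 / 34 / 36%. The gap between arms is 15.0 / 13.6 / 12.3 points, 95% CI ± 10.5 / 11.1 / 11.5.
- c = 20, m = 0 against m = 5: 2 / 5 / 8% against 7 / 11 / 14%. The gap is 4.4 / 5.8 / 6.5 points, ± 5.2 / 6.7 / 7.9.

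At 10 mmHg the count shows the effect imprecisely. At 20 mmHg the expected interval includes zero. Many falls occur with no drug effect, so a single reading must not trigger action.

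**5. People on blood-pressure medication.** If 20 to 40% take such drugs (assumed), there are 24 to 48 per arm. At SD 12 the half-width is 7.0 to 4.9 mmHg and power for 5 mmHg is 29 to 52%. This split can only be descriptive.

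**6. The 20% holding guideline.** At 1:1 allocation the rate in total enrollment is (carnosine + placebo)/2, so the carnosine rate needed is 40% minus the placebo rate. With placebo at 0, 5 or 10% (assumed), carnosine must reach 40, 35 or 30%. The guideline concerns sudden drops and was not built to compare arms.

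**The case against.** The strongest reply is that the harm described in Section 16 is a temporary, sudden drop, and clinic readings at about 6 and 12 weeks will not catch it. That stands. The comparison addresses sustained falls only, and the individual handling in Sections 10 and 14 is still needed. Sections 9 and 10, however, describe lowering of pressure more generally, and that can be sustained.

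A reader might infer that a moderate fall would also go unreported. The documents do not support this. Only Grade 1 is kept off the eCRF, Section 10 lists low blood pressure among the items to be documented, and Section 14 sends all product-related events, whatever their grade, to the DSMB and IRB.

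A reader might also infer that nobody sees safety data by arm. That goes too far as well. The DSMB is unmasked and monitors the distribution of serious events, and sudden drops follow serious-event reporting. The reports are said to include overall totals, which does not rule out other content, and the DSMB charter is not among the documents. The toxicity rule does not say whether its count pools the arms. The 20% criterion is a guideline, and the DSMB may hold the trial for any other reason.

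Finally, aortic systolic pressure comes from the same cuff recording and is probably compared by arm. This narrows the gap without closing it, since that pressure is a derived central measure within an efficacy endpoint whose index is not named.

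**Conclusion.** The point holds in a limited form and is minor. Section 15 has no post-baseline by-arm safety comparison of brachial pressure. A mild or asymptomatic sustained fall that is not recorded as Grade 2 or higher, or as product-related, could go unanalysed as a harm. The gap lies in the pre-specified analysis and the reports as described. It does not lie in the handling of acute drops or in the DSMB's access to allocation, and it does not touch the primary EPC conclusions.

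The planned sample could estimate the effect usefully: within about 2.5 to 3.6 mmHg at 120 per arm, with good to moderate power for 5 mmHg and weak power for 3 mmHg. These figures rest on an assumed SD of change of 10 to 14 mmHg. That the comparison is missing follows from reading the sections and needs no assumption.

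**What to change.** Add to Section 15 a safety analysis of brachial systolic and diastolic pressure at Visits 3 and 4:
- the carnosine-minus-placebo difference with 95% CI, adjusted for the Visit 2 value;
- as support, the number per arm with a fall beyond a size fixed in advance;
- both shown overall and, descriptively, by baseline use of blood-pressure-lowering medication.

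State that the fixed size serves this table only. It does not define a sudden drop, make a reading an adverse event, halt supplement, start serious-event reporting or count towards the 20% guideline.

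Give the DSMB the table by arm with the cumulative report. The principal investigator prepares that report and is blinded, so an unblinded Randomization Committee member should supply the table. Sections 8, 11 and 15 all place a CTU member on that committee.

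Amend the Grade 1 note in Section 13 so that low-blood-pressure adverse events of any grade are entered in the eCRF.

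The cost is SAP wording, one table from readings already taken, and a little data entry. No visit, measurement or participant is added. The sponsor may have to report a modest fall alongside the efficacy results, and the table will show sustained falls, not temporary ones.

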5. EXECUTIVE SUMMARY

[figure not shown]
Study Design: This is a randomized, double-blind, placebo-controlled longitudinal clinical intervention study to assess the physiologic effects of dietary supplementation of carnosine in healthy human participants. Carnosine is a naturally synthesized peptide in the human body, and is also commercially available as a dietary supplement. The primary endpoint in this study are endothelial progenitor cells (EPCs) found in peripheral blood. Exposure to PM_{2.5} is known to decrease levels of EPCs, which represent angiogenesis.

EPCs will be compared between carnosine and placebo groups at 6 weeks and also their change from baseline to 6 weeks to 12 weeks post initiation of intervention. The secondary endpoints are difference in EPCs at 12 weeks between carnosine versus placebo groups and difference in arterial stiffness, endothelial microparticles, and platelet monocyte aggregates between carnosine versus placebo groups at 6 weeks and 12 weeks.

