6. STUDY OBJECTIVES

Primary Objective

The primary purpose of this study is to determine whether taking carnosine as a dietary supplement protects the vasculature from PM_{2.5} air pollution-induced oxidative stress in healthy human subjects. The primary endpoint is difference in EPCs between Carnosine versus placebo groups at 6 weeks and 12 weeks.

Secondary Objective

The secondary objective of this study is to determine whether taking carnosine as a dietary supplement is protective from PM_{2.5} air pollution-induced arterial dysfunction, endothelial damage, and pathological platelet activation in healthy human subjects. The secondary endpoints are difference in arterial stiffness, endothelial microparticles, and platelet monocyte aggregates between Carnosine versus placebo groups at 6 weeks and 12 weeks.

Hypothesis (for Primary and Secondary Objectives)

Carnosine supplementation blunts adverse effects of PM_{2.5} pollution on vasculature of healthy participants.

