Sample Size Computations and Assumptions

The primary outcome measures are EPC-2, EPC -3, EPC -4, EPC -7, and EPC -8. Also, there are many secondary outcome measures. Based on our pilot study, mean and SD (standard deviation) are reported below.

	EPC-2	EPC-3	EPC-4	EPC-7	EPC-8
Mean	0.675783	0.016016	0.050813	0.297092	0.631728
SD	0.702561	0.010805	0.056709	0.412414	0.691299

This is a longitudinal study and primary observations will be made at baseline, 6 weeks and 12 weeks follow-ups. Due to 5 primary outcome measures, we adjusted alpha=0.01 (=0.05/5). Due to multiple sub-studies, we plan to enroll a large evaluable cohort of size n=240. With a correlation of 0.5 on any two consecutive time-point measures, (this is a conservative estimate) and n1=120, n=120 at alpha= 0.01 and power=0.90, we can detect the effect size of 0.5 SD using a two sample t-test in a longitudinal setting. The detectable effects for each EPC is given below.

Power	Correlation	EPC-2	EPC-3	EPC-4	EPC-7	EPC-8
80%	0.50	0.351	0.005	0.028	0.206	0.346
90%	0.50	0.223	0.003	0.018	0.131	0.219
80%	0.80	0.197	0.003	0.016	0.116	0.194
90%	0.80	0.156	0.002	0.013	0.092	0.153

To adjust for attrition/drop out we have increased the sample size to 400.

Associations of PM_{2.5} exposures with measured outcomes will be estimated using mixed effects models. We will use interaction variables to detect whether the association between PM_{2.5} and outcomes is significantly different between with or without carnosine groups. We will perform a formal mediation analysis, which allows for interactions to determine the degree to which carnosine levels mediate the effect of PM_{2.5} on our outcomes. Plots of subject-specific differences over pollution concentrations along with regression plots will be generated.

Sample Size Recommendation

Sample size of 240 participants (120 carnosine supplementation, 120 placebo group) provides sufficient sample size for the primary endpoint as well as other secondary endpoints.

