Due to the prolonged intervention period (12 weeks), two follow-up visits and the inconvenience of taking multiple oral capsules daily, we anticipate a 40% attrition from screening (Visit # 1) through 12-week follow-up (Visit # 4). Therefore, we have established a goal of stratified identification of a total of 400 participants (1:1) at screening (Visit # 1). We anticipate that with a conservative estimate of 60% retention, 120 participants in each group (supplementation, placebo) will complete the entire study.

Multiple Testing Issue

Type I error correction in the context of an early phase clinical trial that performs multiple tests can serve to protect the study interpretation against Type I error inflation. However, the use of corrections for multiple comparisons in “proof-of-concept-studies” is problematic. At this investigational level, tight control of the overall family-wise Type I error rate would increase the likelihood that the investigators would miss a finding of potential importance by attributing it to chance simply because the p-value is large. The study investigators have, in this protocol, attempted to balance the need to control the number of evaluations with the need to identify new effects by not incorporating a multiplicity correction. The primary outcomes measures will be declared significant for alpha <0.01. There will not be any adjustments for secondary outcome measures and will be declared significant at alpha <0.05.

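### The 0.01 level is sized for five tests, but the plan leaves open whether the primary family is five tests or ten (five EPCs at two visits)

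*Combined protocol and SAP*

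**What the plan says.** **The level.** Section 8, Sample Size Computations and Assumptions: "Due to 5 primary outcome measures, we adjusted alpha=0.01 (=0.05/5"). The same paragraph claims 90% power for 0.5 SD with 120 per arm at this level. Multiple Testing Issue, also in Section 8, keeps it: "The primary outcomes measures will be declared significant for alpha <0.01".

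**Both visits primary.** Section 6: "The primary endpoint is difference in EPCs between Carnosine versus placebo groups at 6 weeks and 12 weeks". Section 15, Primary and Secondary Endpoints, opens with "There are 5 primary endpoints: difference in EPCs", names the five EPCs, and continues: "between Carnosine and placebo groups at 6 weeks and 12 weeks. These endpoints will be evaluated at the alpha=0.01". The endpoint lists in Sections 5 and 8 also say that the primary endpoints reflect change to both visits.

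**12 weeks, or each single visit, secondary.** Section 5, Study Design: "The secondary endpoints are difference in EPCs at 12 weeks between carnosine versus placebo groups". Section 15 includes among its secondary endpoints "difference in EPCs between Carnosine and placebo groups at 12 weeks, difference in EPCs between Carnosine and placebo groups at 6 weeks".

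**The test.** Section 15 names a two-sample t-test for the intervention effect. It adds GLM and mixed models for repeated observations without saying which decides the primary question. The trajectory model stands under Additional Analyses.

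**Whether there is a correction at all.** Multiple Testing Issue says none is built in, just before restating 0.01. Multiple Comparisons in Section 15 says none was made and reads p-values at a nominal 0.05.

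**The concern.** A Bonferroni divisor has to count the tests that can each produce the claim. Five is the number of EPC subgroups. If each is compared at 6 weeks and again at 12 weeks, and a success at either visit supports a claim for that EPC, there are ten such tests.

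The plan never states the success rule: either visit, both visits, one named visit, or one test covering both. The first option breaks the link between 0.01 and an overall 5%. The others keep it. An analyst who follows Section 15 literally could report an effect at either visit as a primary finding, with a false-positive risk that the plan has not accounted for. The stated power is tied to the same count, because it was computed at 0.01.

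**Working it through.** **Inputs.** Five EPCs, level 0.01, 120 per arm, effect 0.5 SD and correlation 0.5 between consecutive time points, all from Section 8. Two visits, from Sections 6 and 15. Sidedness is not stated; two-sided is assumed because it reproduces the plan's figure. The correlation between EPCs is not given, so a range is shown.

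**1. The plan's own figures.**
- 0.05/5 = 0.01, exact.
- Expected z for 0.5 SD: 0.5/√(2/120) = 3.873. The two-sided critical value at 0.01 is 2.576.
- Power = Φ(3.873 − 2.576) = 0.903 (noncentral t: 0.898).

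Both figures reproduce, so there is no arithmetic slip.

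**2. Five tests at 0.01.** Bound: 5 × 0.01 = 0.05. If independent: 1 − 0.99⁵ = 0.049. The level does what it was set to do.

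**3. Ten tests at 0.01, either visit sufficing.** Bound: 10 × 0.01 = 0.10. If all ten are independent: 1 − 0.99¹⁰ = 0.096. For correlated tests, ten z-statistics were simulated under no effect, with one common correlation between EPCs, and the share of trials with any |z| > 2.576 was counted:

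| Correlation between EPCs (assumed) | Visit correlation 0.5 | Visit correlation 0.8 |
|---|---|---|
| 0 | 9.2% | 8.0% |
| 0.3 | 8.7% | 7.6% |
| 0.5 | 7.8% | 6.8% |
| 0.7 | 6.4% | 5.6% |
| 0.8 | 5.5% | 4.8% |
| 0.9 | 4.3% | 3.8% |

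Entries are good to about 0.1 percentage point. The second column uses the other correlation tabulated in Section 8.

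**4. Ten tests at 0.01, both visits required.** The same simulation gives at most about 0.5% (visit correlation 0.5) or 1.7% (0.8). Five shares are more than enough.

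**5. Level and power for a family of ten.**
- 0.05/10 = 0.005; bound 0.05 (0.049 if independent). The critical value is 2.807.
- Power for 0.5 SD at 120 per arm = Φ(3.873 − 2.807) = 0.857 (noncentral t: 0.849), so about 85%.
- Restoring 90% takes 134 per arm by the normal formula (136 by noncentral t). That is 268 evaluable and 268/0.6 ≈ 447 randomized at the planned 40% attrition, against 400.

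**6. Holm in place of the fixed split, five tests, 0.5 SD (simulated).** Average power per responding EPC, against 0.90 for the fixed split: 0.90 if one EPC responds, 0.92–0.93 if three respond, 0.94–0.97 if all five respond.

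**The case against.** The strongest reply is that the plan can be read as having exactly five primary tests. Section 15 counts five primary endpoints and lists the separate 6-week and 12-week EPC comparisons as secondary. Section 5 makes 12 weeks secondary. Section 8 describes its power calculation as set in a longitudinal design. With one visit, one longitudinal contrast per EPC, or a rule that both visits must succeed, 0.05/5 is adequate. This stands as far as it goes: ten tests is one reading, not a settled fact. It does not close the point, because Sections 6 and 15 also put both visits in the primary endpoint and nothing chooses between the readings.

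A second reply is that high correlation between EPCs would hold the error near 5% anyway. That is possible: the rate falls below 5% at a common EPC correlation of about 0.85 (visit correlation 0.5) or 0.8 (visit correlation 0.8). EPC-2 and EPC-8 have similar pilot means and SDs, but that does not establish correlation, and the documents give no value.

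A third is the argument in Section 8 that tight family-wise control does not suit a proof-of-concept study. That is a defensible position. However, the same paragraph then retains 0.01 for the primary outcomes, and the sample size rests on it.

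A reader might also infer that the fixed 0.01 is itself a mistake because Holm's step-down rule is at least as powerful. The documents do not support that. A fixed Bonferroni split is valid, the planned power was computed with it, and Holm gains essentially nothing when only one EPC responds.

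**Conclusion.** The concern holds conditionally. The primary time point and success rule are not fixed, and under one natural reading of Sections 6 and 15 a level sized for five tests is spent on ten. In that case only the 10% bound is certain. The actual rate is roughly 4% to 9%, assuming two-sided tests, a visit correlation of 0.5 and a common EPC correlation between 0 and 0.9.

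A reader might conclude that the trial's false-positive risk is well above 5%. That goes too far: it needs the either-visit reading and EPCs that are not very highly correlated, and the documents settle neither. The division of 0.05 by five and the 90% power are both correct for five tests.

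The disagreement between 0.01 and a nominal 0.05 is a separate matter and larger in size. At 0.05, independent tests would give 1 − 0.95⁵ = 23% for five and 1 − 0.95¹⁰ = 40% for ten. Settling it in favour of 0.01 would still leave the count of five or ten open, so both need attention.

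**What to change.** Before unblinding, choose one of these and state it in the same words throughout:

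- **Preferred.** Name one primary visit, or one contrast averaged over the two visits, for each EPC, and make the other single-visit comparisons secondary. The family is five, 0.01 stands, and so does the 90% power for 0.5 SD at 120 per arm. With the averaged contrast, the 0.5 SD has to be the effect averaged over both visits.
- **If both visits stay primary and either suffices.** Define a family of ten with a first threshold of 0.005. Restate the power for 0.5 SD at 120 per arm as about 85%, or plan for about 134 per arm (about 447 randomized).

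Then reconcile the Study Design text in Section 5, the Primary Objective in Section 6, the sample size and Multiple Testing Issue text in Section 8, and the endpoint and Multiple Comparisons text in Section 15. This includes the statements that no adjustment is made and that p-values are read at 0.05.

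Optionally, apply Holm at overall two-sided 0.05 over the chosen family. It controls the same error and never rejects less than the fixed split, with a gain only when several EPCs respond. This is an improvement, not the correction of an error; its small drawback is that simultaneous confidence intervals remain the Bonferroni ones.

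The preferred option costs a few sentences spread over these sections and no additional data or participants. The second costs about five points of stated power, or about 47 more randomized participants.
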